Human Subjects Involvement, Characteristics and Design: The goal of this research is improve developmental outcomes in infants who have undergone congenital heart surgery. Infants who require surgical correction of congenital heart defects are often treated with hypothermia during the surgery to protect the brain. Following completion of congenital heart surgery, the current standard of care is to rapidly rewarm them on cardiopulmonary bypass to normothermia. This rapid rewarming is thought to have adverse effects on the brain. This project proposes to partially rewarm infants to 35°C on bypass and then complete rewarming over the first 12 hours after surgery in the intensive care unit using an FDA approved machine that can carefully control body temperature changes by small increments. In this project, safety of the

“delayed rewarming” technique will be assessed and we will ultimately aim to assess efficacy in a larger future trial if safety can be shown first.

The study of human subjects is therefore necessary to achieve the goals presented in this application. The proposed clinical research for specific aims 1 and 2 will involve human subjects prospectively recruited from Maine Medical Center located in Portland, Maine. As the only pediatric tertiary care center in the state, the catchment area is large. Included subjects will be less than 12 months of age. Each subject must undergo congenital heart surgery with cardiopulmonary bypass before the age of 12 months. We aim to recruit 30 infants over a 24 month period. It is expected that there will be an equal proportion of male and female subjects. It is expected that the racial and ethnic composition of subjects will reflect the racial homogeneity of the state of Maine.

Infants will be randomized to one of two groups; the standard of care group versus the experimental group. Infants in the experimental group will receive the delayed rewarming therapy, which consists of stopping rewarming on bypass at either 35 °C and gradual rewarming over 12 hours to normothermia through use of a servo-controlled temperature regulating blanket. Adverse events such as effects on hemodynamic status, coagulation status, rate of infection and incidence of subcutaneous fat necrosis will be compared between groups as will serum biomarkers of neuronal injury.

In terms of research subjects, infants with congenital heart disease are considered a vulnerable population and the proposed use of this vulnerable population requires additional justification. Infants with congenital heart disease are not only vulnerable in a research sense, but also in a clinical sense. These infants could not survive without the surgical procedures we have the capacity to perform. Yet, ironically in the face of these tremendous surgical advances, neurodevelopmental outcome remains suboptimal. It is well-established that hypothermia is well tolerated in a different population of infants, namely newborns with suspected hypoxic ischemic brain injury. Multiple safety and efficacy trials have been performed and have shown that not only do these infants tolerate therapeutic hypothermia with exceedingly infrequent complications, but they also demonstrate better developmental outcomes than would otherwise be anticipated based on the clinical history of their births. Infants with congenital heart disease must be studied directly in the clinical setting in order to ascertain whether or not they might benefit in terms of developmental outcomes in the same manner. Before efficacy of the intervention can be assessed, safety must first be demonstrated. Animal models would be inadequate both due to an inability to recreate surgical heart lesions in rodents or other mammals and due to the inability to fully translate animal developmental outcomes into human outcomes.

Sources of Materials: For this protocol, the frequency of adverse events will be compared between the standard of care group and the experimental group across 5 specific areas as follows: hemodynamic status, coagulopathy, infection, hyperthermia and subcutaneous fat necrosis (see next section for full details). The current standard of care for intensive care unit monitoring is adequate to monitor for adverse events in both the standard of care and experimental groups. Adverse events will be clinically apparent and both the event and medical management will be documented in the infant’s medical record. Continuous vital signs (temperature, heart rate, blood pressure, respiratory rate and oxygen saturation) will be monitored and recorded by the nurse caring for the patient as well as all usual standard post-operative laboratory and imaging studies. These will include laboratory tests for evidence of renal dysfunction, coagulation studies and chest x-rays monitoring for infection and fluid accumulation. The equipment used to provide delayed rewarming to the 15 infants in the experimental group will be purchased by the research study.

In order to protect the subject information described above, HIPAA standards will be adhered to and data that is kept will be de-identified. Each participant will be assigned an individual participant number and names and medical records will not be used. All paper documentation will be kept in a secure file in a locked area and will ultimately be scanned to pdf and stored on a secure and encrypted server. When

creating the REDCap data base, the subject number will be used as the principal identifier. [name] and her Research Coordinator, [name] will be the only persons with access to the key which encodes the subject name with the demographic and other information.

Potential Risks: There are potential risks to the critically ill subjects enrolled in this study, the most significant of which are outlined below:

6. **Hemodynamic status**-Infants who are hypothermic typically have lower resting heart rates than those who are normothermic (80-100 beats per minute and 120-140 beats per minute respectively). In the post-operative congenital heart infant, bradycardia (slow heart rate) could conceivably have an adverse impact on the hemodynamic status of the infant and if untreated this could also impact kidney function. Hemodynamic status will be monitored and intravenous medications to support cardiac function and blood pressure (which these infants are typically already treated with) will be up-titrated if necessary.
Normothermic post-operative congenital heart infants may experience a cardiac arrhythmia following surgery known as junctional ectopic tachycardia (JET). JET is a surgical complication that is concerning due to the fact that the newly repaired heart is beating significantly faster than it is intended to, adding significant strain to the heart muscle and potentially compromising hemodynamic stability. One of the treatments for JET is to reverse **hyperthermia** (this is only an option if the patient has a fever) or potentially even use **hypothermia** for refractory cases. We will monitor carefully to determine whether or not there is a decreased incidence of JET in the delayed rewarming group.
7. **Coagulopathy**- In adults who undergo therapeutic hypothermia following cardiac arrest, there is evidence of coagulation dysfunction and subsequent risk of bleeding. This tends to not be the case in infants who tolerate therapeutic hypothermia better than adults. Laboratory screening for coagulopathy will occur and if coagulopathy develops, blood products (Platelets or Fresh Frozen Plasma or Cryoprecipitate) will be administered to reverse this.
8. **Infection**- In adults, there is evidence for increased rate of ventilator acquired pneumonia in patients undergoing therapeutic hypothermia after myocardial infarction. Again, this is unusual in infants who tolerate hypothermia better. The infants in this study will receive daily chest x-rays in the post-operative setting and signs of infection will be carefully monitored for and antibiotics started if necessary.
9. **Hyperthermia**-The infant's temperature will be closely monitored through use of a rectal temperature probe during the delayed rewarming process. A rectal probe must be used due to the fact that a skin recording is less accurate with hypothermic patients.
10. **Subcutaneous fat necrosis**-In infants who are exposed to a full 72 hours of therapeutic hypothermia, there is a rare complication of breakdown of the fat stores in the skin leading to the formation of fluid filled nodules in the skin that are unsightly but not life threatening. These nodules typically resolve without intervention over the weeks following the hypothermia exposure. Good hemodynamic status is protective against this complication. It is expected that the short duration of rewarming (only 12 hours) will not cause any incidents of subcutaneous fat necrosis.

The alternatives to the proposed delayed rewarming treatment are to continue to offer only the standard of care treatment of rapid rewarming on bypass. This standard of care of rapid rewarming is suspected of having a contribution to the cognitive deficits and neurological dysfunction experienced by patients after congenital heart surgery and cardiopulmonary bypass. Given that it is known that newborn infants with hypoxic ischemic brain injury have essentially no adverse events related to hypothermia, it is reasonable to try this delayed rewarming approach to see if it will be safe in infants following congenital heart surgery. There is a research publication on children ages 6-15 years with congenital heart disease who were treated with delayed rewarming after cardiopulmonary bypass. In this age group, there were no statistically significant differences in adverse events between the delayed rewarming and standard of care groups, but a definite improvement in the cognitive performance of children in the delayed rewarming group. The fact that this delayed rewarming technique has been shown already to be safe and effective in an older population

of children in the post-operative setting with congenital heart disease also makes it reasonable to test this technique in younger children.

The privacy risk to participating subjects is deemed to be minimal and certainly not in excess of that risk incurred with receiving medical care in the first place.

ADEQUACY OF PROTECTION AGAINST RISKS:

Recruitment plan and consent procedure: The pediatric cardiology team and pediatric cardiothoracic surgeon will refer appropriate patients to the principal investigator (PI) for consideration of enrollment. The PI will meet with families in the outpatient setting to obtain consent prior to the admission during which the congenital heart surgery will be performed. For infants born who need congenital heart surgery within the first few days of life, the PI will obtain consent from parents in the hospital prior to surgery. The envelopes for randomization will be opened at the time consent is obtained to insure that there is adequate time to arrange for the type of post-operative care the infant will receive (intervention versus standard of care).

Before infants are accepted into the study, the parent or guardian must:

- give oral and written consent
- be aware of alternative treatments, and that alternative clinical care is available;
- be aware of the right to withdraw

In a private location, following discussions about informed consent with the parent/guardian, we will ask the parent or guardian to sign an authorization to participate in research and permission to use or release protected health information (informed consent). Parents of potential participants who do not comprehend or speak the English language will be offered a personal translator through Maine Medical Center's (MMC's) language bank.

The inclusion criteria specify that all participants will be both male and female infants under the age of 12 months with congenital heart disease requiring cardiopulmonary bypass for surgical correction. All ethnic groups will be eligible. Subjects will be recruited only from Maine Medical Center.

Exclusion criteria specify that infants with known coagulopathy or those not requiring cardiopulmonary bypass or hypothermia during surgery will not be enrolled.

Protection Against Risks: The Institutional Review Board (IRB) at Maine Medical Center will oversee the safety of subjects in this research study. Initial approval is required before the study is initiated and during its conduct.

Risk for adverse effects of the delayed rewarming strategy will be monitored by a drug safety and monitoring plan (see below). Adverse events will be reported to the members of the monitoring board and the interpretation of these events being related to the delayed rewarming intervention will be made by members of the board.

Potential Benefits of the Proposed Research: There are significant potential benefits to the subjects in this research. Current practice for post-operative pediatric congenital heart patients at Maine Medical Center includes rapid rewarming, which is thought to contribute to cognitive dysfunction and neurological abnormalities. The delayed rewarming technique proposes to ameliorate this effect although this study is not powered to demonstrate this. In addition, infants may not experience an arrhythmia (junctional ectopic tachycardia) as a result of better temperature regulation that prevents **hyperthermia** and may have better cardiac performance as a result of this. If infants have seizures, these will be better recognized and treated

with 48 hours of continuous EEG in the post-operative setting. If development is adversely affected, early developmental assessment could lead to earlier referral for therapy which may help outcome.

Importance of the Knowledge to be Gained: Cognitive and developmental outcomes for infants following congenital heart surgery are suboptimal in many cases. The proposed delayed rewarming strategy uses an FDA approved device for an approved indication in a new population of patients. If the delayed rewarming strategy is safe and well-tolerated, subsequent studies will be designed to assess efficacy. We believe that this research is greater than minimal risk but presenting the prospect of direct benefit to the individual child and to the population of infants with congenital heart defects (according to 45 CFR 46.405). It is also conceivable that the delayed rewarming strategy could be implemented in children and adults in similar post-operative settings.

Data Safety and Monitoring Plan: Three independent medical monitors have been appointed for this study to review clinical events in real time to allow timely, unbiased decision-making regarding study risk. The data safety monitoring board (DSMB) will consist of [name], attending pediatric cardiologist, [name], attending pediatric neurologist and [name], attending pediatric intensive care physician. None of these three physicians were directly involved in the design or implementation of this research study and are therefore as unbiased as one can be in the assessment of safety. They have been selected to serve on the DSMB due to their combined experience and ability to critically assess clinical scenarios. The PI will report any adverse event to the monitoring entity with 24 hours and any other care provider to the infant will have the ability to report adverse events as well. The Data Safety Monitoring plan will follow the procedures and policies outlined by the Human Research Protection Plan at Maine Medical Center (MMC). This plan requires that the study be reviewed by the Maine Medical Center Institutional Review Board (IRB), and upon approval the conduct of the study will adhere to the Good Clinical Practice Standard Operating Procedures for Good Clinical Practice in the Conduct of Clinical Research at MMC. A Study Coordinator from the MMC Clinical Trials unit will be monitoring on a continuous basis the collection of study data for this research project. The Study Coordinator will maintain all regulatory files and ensure that all data collection is monitored against source documentation. The Study Coordinator will also ensure proper monitoring for adverse events as well as protocol deviations, following guidelines contained in the Clinical Practice Standard Operating Procedures for Good Clinical Practice in the Conduct of Clinical Research at MMC.

Definitions of Adverse Events and reporting to DSMB

Table 1: Definitions of Serious, Moderate and Other Adverse Events

Serious Adverse Events	Reported to DSMB within 24 hours of occurrence
Mortality	Death within 48 hour period following surgery
Need for resuscitation	Need for cardiopulmonary resuscitation within 48 hours of surgery
ECMO after surgery	Persistent need for bypass (ECMO) following surgery; STUDY EXCLUSION CRITERIA
Return to OR on day of surgery	Unexplained hemorrhage prompting return to the OR for exploratory surgery
Stroke or seizures	Ischemic or hemorrhagic stroke OR status epilepticus OR clinical or electrographic seizures
Moderate Adverse Events	Reported to DSMB within 48 hours of occurrence
Bradycardia	Clinically significant heart rate <100 bpm for >30 minutes*
Tachycardia	Clinically significant heart rate > 160 bpm for 30 minutes*
Arrhythmia (JET)	Any occurrence of JET(Junctional ectopic tachycardia) OR other arrhythmia
Hypotension	Systolic BP< 70 mm Hg OR Diastolic BP< 30 mm Hg *
Coagulopathy	INR > 2.2 OR PTT > 74 seconds Thrombocytopenia with platelets < 50,000 Chest tube output more than 5 cc/kg/hr OR 40 cc/kg in an 8 hour shift
Leukopenia	White blood cell count < 4,000
Other adverse Events	Reported to DSMB within 7 days
Hypertension Pressor Use Days of intubation Infection Subcutaneous fat necrosis	Systolic BP > 100 mmHg OR Diastolic BP > 80 mmHg* Treatment with more than 2 pressors for more than 7 days Intubated for longer than 5 days Occurrence of urinary tract infection, pneumonia OR other wound infection Any occurrence

*resulting in hemodynamic compromise and/or need to administer medications to support heart rate and/or blood pressure

Stopping Rules: DSMB has the responsibility of pausing or stopping the trial in the case of 1) any serious adverse event probably or definitely related to study intervention OR 2) two or more unexpected or unanticipated adverse events of same or similar type

Adequacy of sample: We aim to enroll 30 infants and randomize 15 to the standard of care and 15 to the experimental group. With 15 infants in each group, we have determined that we will not have the necessary power to permit definitive analysis of the results, but will use these preliminary data to establish whether or not the treatment is safe and well-tolerated for the design of future, larger adequately powered trials.

Inclusion of Women and Minorities: The recruitment for this study requires that infants have a diagnosis of congenital heart disease requiring surgical palliation. The incidence of congenital heart disease is estimated at 1 percent of births in the United States or 40,000 infants per year. In Maine, there are nearly 13,000 births annually and the possibility of 130 new infants each year with congenital heart disease. Surgery with cardiopulmonary bypass is performed only on the most severely affected and estimated at approximately 60 per year under the age of 12 months. As the incidence of this disease is random, so too will be the distribution of affected boys versus girls. The parents of every child with severe congenital heart disease will be approached for participation and this is feasible since our institution is the only hospital in the state where these surgeries can be performed. Maine is a homogenous state with respect to minorities, but we do however have increasing immigrant and refugee populations which will be approached equally. The PI will work to ensure that there are no disparities in the recruitment of boys versus girls or of Caucasian versus minority infants.

Inclusion of Children: Congenital heart disease occurs in children and often requires surgical palliation within the first 12 months of life. These infants who undergo surgery for congenital heart disease are at risk for cognitive and neurological dysfunction due in part to the side effects of the very procedures they require in order to sustain life. It is necessary to prospectively enroll infants with congenital heart disease who have undergone corrective surgery to determine whether or not delayed rewarming is safe and well-tolerated to permit future study of the efficacy of this technique. All subjects enrolled in this study will be infants under the age of 12 months.

The PI has experience in clinical research with neonates and extensive clinical training providing her with the expertise necessary to enroll and safely monitor the neurological care of these infants.

Bibliography:

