2.1 Compare levels of serum biomarkers of brain injury in the acute post-operative setting including serum s100b and NSE (neuron specific enolase). Levels will be assessed in both groups in the pre-operative setting for baseline and

serially in the post-operative setting for 72 hours. It is hypothesized that infants in the “delayed rewarming” group will show a trend toward lower levels of biomarkers of brain injury.

[figure not shown]
2.2 Record EEG and monitor seizure frequency in infants for 48 hours following CHD surgery. Seizures, if they occur, will be treated in both groups and the duration quantified in seconds. EEG is needed primarily to rule out potential confounding effects of seizures on later developmental outcome. It is hypothesized that there will be infrequent seizures and no differences in seizure frequency or duration between groups.

2.3 Compare developmental outcomes using Bayley Scales of Infant Development (Bayley 3). Bayley testing will be performed on infants at either 6 or 12 months of age depending on the infant’s age at the time of surgery. It is hypothesized that infants in the “delayed rewarming” group will show a trend toward improved Bayley scores compared to the standard of care group.

Preliminary data:

A retrospective review of cases of congenital heart disease requiring surgical palliation was performed for cases from January 2011 to May 2014. The database was provided by [name] to [name] for the purposes of this analysis. This database is kept for quality work in [name] office. Please see the attached letter of support for this project from [name]. In this review, there were 191 surgeries performed on infants under the age of 12 months by [name] in the 41 month interval (average 4.6 surgeries per month). Some infants required multiple surgeries and therefore the total number of surgeries (191) reflects 119 individual infants. The proposed research project includes only infants undergoing cardiopulmonary bypass (CPB) for the first time. In this sample, there were 88 CPB surgeries. Ten infants had surgery requiring CPB on more than one occasion and thus eliminating repeat exposures to cardiopulmonary bypass, 76 of the 88 total surgeries would have met inclusion criteria for enrollment into this research project (1.9 infants per month or 22 per year). Anticipating a 2 year period of recruitment, there should be approximately 44 eligible infants and we will seek to enroll 30.

[figure not shown]

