Figure 3b: Research design for KL2 project

Randomization: We will randomize in a one to one fashion. A random number generator will be used with those numbers being translated into a list of sequentially numbered opaque envelopes that will be opened by the principal investigator (PI) in order at the time of randomization following the informed consent process.

Recruitment: [name] and [name] are pediatric cardiologists and follow expectant mothers weekly or biweekly throughout a pregnancy known to be complicated by a diagnosis of congenital

heart disease. [name] and [name] will refer appropriate patients to [name] (PI) for consideration of enrollment. The PI will meet with the pregnant mother and father in the outpatient setting several weeks after the diagnosis has been made, giving the family time to come to terms with this new diagnosis. At the first meeting with the PI, the family will be informed about the research study and given informational handouts. Another meeting will occur prior to the admission during which the congenital heart surgery will be performed. At this second meeting, informed consent documentation will be reviewed and signatures obtained from parents willing to participate. For infants who need congenital heart surgery within the first few days of life or for those in whom a fetal diagnosis was not made, the PI will obtain informed consent from parents in the hospital prior to surgery. The envelopes for randomization will be opened at the time consent is obtained to insure that there is adequate time to arrange for the type of post-operative care the infant will receive (intervention versus standard of care).

Standard of care group: For infants assigned to the standard of care group, the congenital heart surgery will be performed according to usual practice with the degree of intra-operative hypothermia determined by the cardiothoracic surgeon and his team based on the anticipated complexity of the case. Following completion of the surgical procedure, the infant will be rapidly rewarmed on cardiopulmonary bypass at a rate of 1°C each 3-5 minutes. The infant will achieve normothermia of 36-37°C and be transported to the Pediatric Intensive Care Unit (PICU) for routine post-operative monitoring. Standard of care procedure in the post-operative setting is clearly defined below on Figure 4.

Figure 4: Standard of Care Temperature Management after Bypass

LOCATION	PERSON RESPONSIBLE	RECORDING SITE	GOAL TEMP	FACTORS

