2. Residual blood that would otherwise be wasted from a clinically obtained sample will be collected and used for testing for biomarkers of neuronal injury (s100b and NSE). These samples will be obtained at the following 5 intervals; the pre-operative setting for baseline, post-operatively after bypass, at post-op hour 24, at post-op hour 48 and at post-op hour 72. [name], Research Program Director of the BioBank and Research Laboratory Services (RLS) at Maine Medical Center Research Institute has kindly agreed to assist with technical support for the processing of the s100b and NSE testing. The s100b testing is a serum ELISA test run on a kit provided by Millipore™. This test requires 100µL of serum per sample to be tested. This ELISA may be run on a sample that has been previously frozen. The NSE test is also run on serum and is an ELISA test requiring 100µL of serum that may also be used on a frozen stored specimen. The company providing the NSE sample kit is R&D Systems. The stored samples will then be run in batches once the full collection period is complete. The collection of the samples and the handling of samples will be facilitated by the PI and [name], research

coordinator participating in the project (please see the attached letter of support from [name], VP Neuroscience Service Line who is funding the research coordinator position).

3. Bayley Infant Scales of Development (Bayley 3) will be performed between age 9 months and 2 years. The testing will be performed by a physical therapist who assesses fine and gross motor indices and by a Master's level psychologist who assess both the cognitive and language development components. Severe developmental disability will be defined as a Bayley Mental Development Index score that is 2 standard deviations below the mean score (eg. below 70)⁵. Moderate developmental disability will be defined as a Bayley Mental Development Index score that is 1 to 2 standard deviations below the mean score (eg. below 70-84)⁵. The parents of research subjects will have the opportunity to meet with a member of the developmental assessment team to review results of the testing.

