Experimental group: For infants assigned to the experimental group, the congenital heart surgery will be performed according to usual practice as detailed in the standard of care group section above, with depth of hypothermia dictated by the complexity of the congenital heart lesion to be repaired. Upon completion of the surgical procedure, partial rewarming will occur on cardiopulmonary bypass, but will stop when the infant reaches 35°C.

The infant will be transported from the operating room to the PICU at 35°C and placed on a servo-controlled blanket with an esophageal temperature probe placed. Through use of the servo-controlled blanket, the rate of rewarming will be carefully regulated with increases in temperature of 0.3°C every 2 hours for 6 and then of 0.2°C every 2 hours for 6 hours to the goal temperature of 36.5°C (see Appendix 1 for temperature management worksheet phase 1). The intensity and frequency of post-operative monitoring will be exactly the same in the experimental group as in standard of care group, including post-operative EEG, serum biomarker testing and neurodevelopmental follow up. The following parameters will be observed in the experimental group and compared with the standard of care group.

1. Hemodynamic status-Infants who are hypothermic typically have lower resting heart rates than those who are normothermic (80-100 beats per minute versus 120-140 beats per minute respectively). In the post-operative congenital heart infant, bradycardia (slow heart rate) could conceivably have an adverse impact on the hemodynamic status of the infant and if untreated this could also impact renal function. Hemodynamic status will be continuously monitored in the same manner as detailed in the standard of care section. Intravenous medications to support cardiac function and blood pressure (which these infants are typically already treated with) will be up-titrated if necessary. The need for permanent pacemaker implantation will be documented.

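### No step keeps the treatment arm from the two assessors who give and score the Bayley, so this secondary outcome is open to assessor bias that simple masking would reduce

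*Combined protocol and SAP*

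**What the plan says.** The Bayley is the third listed departure from routine care under Materials and Methods, Standard of care group. Two people give it: "The testing will be performed by a physical therapist who assesses fine and gross motor indices", and the rest is done "by a Master's level psychologist who assess both the cognitive and language development components". The Experimental group section says that monitoring is the same in both arms, "including post-operative EEG, serum biomarker testing and neurodevelopmental follow up". Neither section says whether the assessors know the arm, and no other section mentions masking of assessors, parents or data.

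On allocation, the Randomization paragraph provides for "sequentially numbered opaque envelopes that will be opened by the principal investigator (PI) in order at the time of randomization". The Recruitment paragraph adds: "The envelopes for randomization will be opened at the time consent is obtained". The reason given is to allow time to arrange arm-specific care. After surgery the experimental infant is "placed on a servo-controlled blanket with an esophageal temperature probe placed". Sources of Materials says that vital signs, including temperature, are recorded and that the management of adverse events is documented in the medical record.

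Specific Aim 2.3 states the hypothesis that "infants in the “delayed rewarming” group will show a trend toward improved Bayley scores compared to the standard of care group". The only role given to parents in the Bayley section comes afterwards: "The parents of research subjects will have the opportunity to meet with a member of the developmental assessment team", to go over the results. Anticipated outcomes lists developmental assessment among the secondary outcomes.

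**The concern.** The Bayley is administered and scored by an examiner, so it leaves room for judgement. An examiner who knows the arm and the study's hypothesis may, without intending it, prompt or score more generously in one direction. Opaque envelopes do not prevent this. They conceal the allocation before assignment and mask nobody afterwards.

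The assessors could learn the arm in two ways. Parents were there when consent was given and the envelope opened, so they probably know it and may mention it. The medical record would also show how the infant was rewarmed. The plan closes neither route.

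The plan looks only for a trend in Bayley scores. It gives no threshold for one, and the Analysis section names no method for this outcome. A reading that rests on direction alone is sensitive to a small systematic shift. More infants or later pooling would average out chance variation but not a shift of this kind, and it cannot be corrected once the scores have been collected.

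**Working it through.** The plan gives no effect size, significance level or power for the Bayley, so there is no figure of its own to reproduce. The calculation below only shows the scale of the problem.

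**Inputs**
- Infants per arm: 15 (Adequacy of sample).
- SD: 15 points. The Bayley section places 2 SD below the mean at 70. If the mean is 100, which the plan does not state, SD = (100 − 70)/2 = 15. The moderate band of 70-84, covering 1 to 2 SD below the mean, is also 15 points wide. The SD in this population is not given; a larger one would make the ratios below smaller.
- Scoring shift in favour of delayed rewarming: 3 to 5 points, with 2 and 7.5 as wider limits. These are assumptions.

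**Standard error of the difference in means**

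SE = SD × √(2/n) = 15 × √(2/15) = 5.48 points.

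**Shift relative to the standard error**

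3/5.48 = 0.55 and 5/5.48 = 0.91.

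**Chance that the observed difference favours delayed rewarming when there is no true effect**

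P = Φ(shift/SE), normal approximation.

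| Assumed shift (points) | 15 per arm (SE 5.48) | 10 per arm tested (SE 6.71) |
|---|---|---|
| 0 | 50% | 50% |
| 2 | 64% | 62% |
| 3 | 71% | 67% |
| 5 | 82% | 77% |
| 7.5 | 91% | 87% |

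The last column assumes that some infants are not tested; 10 per arm is not a figure from the plan.

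**Precision without any bias**

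The 95% interval has a half-width of 1.96 × 5.48 = 10.7 points. With a two-sided 5% level (assumed), the difference detectable with 80% power is (1.96 + 0.84) × 5.48 ≈ 15.3 points. So a shift of 3 to 5 points would seldom produce a nominally significant result in favour of delayed rewarming (8% to 15% of the time, against 2.5% with no shift). It would often set the direction of the difference, and direction is what a trend describes.

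**The case against.** Several arguments on the other side have force.

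- **Silence is not proof of unmasked testing.** The assessors are a therapist and a psychologist, not the principal investigator or the intensive care staff. Nothing says that they are given the allocation or read the surgical record. The intervention is over about a day after surgery, so the infant would not normally reveal the arm at testing. This stands, and it limits the point: the plan does not require masking, and without a record of it nobody could show afterwards that it was achieved.
- **Parents at testing.** A reader might infer that parents who know the arm sit in on the test. The plan says neither that they attend nor that they are told the arm. Their knowledge is likely, because the envelope is opened at consent, but their attendance is not documented. Nor does the plan say where testing takes place.
- **Role in the next trial.** A reader might infer that a Bayley trend will trigger the efficacy study. The plan does not support this. Human Subjects Involvement, Characteristics and Design, and Importance of the Knowledge to be Gained, both make safety the condition. The main hypothesis in Background and Hypothesis pairs safety with a biomarker trend, not a Bayley trend.
- **Noise dominates.** With a half-width of 10.7 points, a directional trend is weak evidence even with perfect masking, and the plan disclaims definitive analysis. This stands, and it limits how much weight the point can carry. It does not excuse a systematic shift, because the two errors add.
- **Other defects in this outcome.** Specific Aim 2.3 sets testing at 6 or 12 months, the Bayley section at 9 months to 2 years, and the Analysis section names no Bayley method. These are separate points that also need to be reconciled.

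**Conclusion.** The point holds in a limited form. The plan contains no step that keeps the arm from the people who give and score the Bayley, although the arm can be learned and the hypothesis is directional. On the stated assumptions (15 per arm, SD 15, shift of 3 to 5 points), the bias would be 0.5 to 0.9 of a standard error, and the chance of a falsely favourable direction would rise from 50% to about 71-82%. The shift is assumed, and nothing in the plan shows that bias of this size, or any bias, will occur.

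This is a secondary outcome of a safety pilot. The primary safety comparison does not depend on it, and neither does the stated condition for the next trial. The Bayley data are supporting information for a later study of development. The change is worth making because it is cheap and cannot be made after the scores exist. It should not be described as removing the bias, since a parent may still disclose the arm.

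**What to change.** Add a paragraph to the Bayley item under Standard of care group, applying to both arms:

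- The therapist and the psychologist are not told the arm, and do not consult records that reveal it before scoring.
- The coordinator books visits by study ID. Study IDs already exist for data handling, and Sources of Materials already restricts the key to the principal investigator and the coordinator.
- Parents are asked not to disclose the arm before or during testing.
- Scores are entered and locked before results are discussed with the family.
- Each assessor records whether the arm became known, and how. The number of such cases is reported by arm with the Bayley results.

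The restriction should cover only records that reveal the arm; barring the whole medical record would be broader than necessary.

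Cost: a small amount of coordinator work, with the same assessors and visits and no change to sample size or care. The plan gives no cost figure. Masking may be incomplete if parents disclose the arm, which is why unmasking should be recorded.
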